## **2.8.4 Other safety data**

### **2.8.4.1 ECG and cardiac imaging data**

[figure not shown]
An ECG will be taken at Screening and recorded in source documents. ECG will not be reported in the CSR.

[figure not shown]
#### **2.8.4.2 Vital signs**

Summaries of vital signs data will include treatment-emergent measurements, which are defined as measurements taken post-baseline and up to the last study visit.

Absolute values and change from baseline (where applicable) will be summarized for vital sign parameters (height, weight, temperature, pulse rate, systolic blood pressure, diastolic blood pressure, and respiratory rate) by treatment group, visit and time point including the minimum and maximum treatment-emergent value.

The baseline value is the last value prior to first dose of double-blind treatment.

## 2.11 Interim analysis

No interim analysis is planned. A DMC at Novartis will be established to conduct periodic semi-blinded or unblinded safety reviews to monitor safety data. The DMC analysis does not inflate the Type I error for the primary efficacy hypothesis testing. Thus no adjustment for multiplicity is required.

More details will be outlined in the DMC charter and a separate DMC SAP.

## 3 Sample size calculation

Assuming a true treatment difference in proportion of patients meeting the primary composite endpoint of 15% for ruxolitinib added to SoC therapy compared to placebo added to SoC therapy, a sample size of approximately 402 participants provides at least 80% power that the primary analysis will be statistically significant at the two-sided 5% significance level. This holds for a variety of different assumptions with respect to the proportion of patients meeting the primary composite endpoint ([Table 3-1](#)).

These sample size assumptions were evaluated in East Version 6.4.

**Table 3-1 Sensitivity of sample size assumptions to different proportion of patients meeting the primary composite endpoint for level of significance  $\alpha = 0.05$**

Proportion of patients meeting the primary composite endpoint in placebo + SoC (%)	Proportion of patients meeting the primary composite endpoint in ruxolitinib + SoC (%)	Power (%)
80	65	91
70	55	85
60	45	82
50	35	82
40	25	85
30	15	91

## 4 Change to protocol specified analyses

The analysis of the primary endpoint is the same as in the protocol. However, the handling of missing data for the primary composite endpoint is worded differently from the protocol. As the protocol allows patients to be treated for 14 or 28 days some of the patients will not be treated for the entire study period of 29 days because they have recovered and/or been discharged or the investigator feels they would not benefit from further double-blind treatment. Such cases did not “discontinue from the double-blind treatment”, but they actually “completed the planned treatment”. The off-treatment measurements collected should be used in the analysis (which did not change from the protocol) wherever available, as the outcome is still valid as a result of the previous treatment. In addition, the off-treatment data collected for other patients will also be used, from an intention-to-treatment perspective. The rationale of the missing data handling is made clearer in the SAP.

In Section 12.3 of the protocol, it was mentioned that significant non-drug therapies will be summarized according to the ATC classification system. However in the SAP, we specify that surgical and medical procedures will be summarized by primary SOC and PT, as ATC classification is not available for non-drug therapies.

In Section 12.4.2 of the protocol, it was mentioned that baseline clinical status based on the 9-point scale ( $\leq 4$ ,  $\geq 5$ ) will be included as a covariate in the primary analysis model. In the SAP, we have changed the categorization of the score to be ( $\leq 3$ ,  $\geq 4$ ). This is because very limited patients were recruited with baseline clinical status of 5 and the potential issues it may cause in the modeling.

In Section 12.5.1 of the protocol, it was mentioned that country will be used as a covariate. However, we have modified in the SAP that region will be included instead. This will avoid potential modeling issues due to small sample size in some of the countries.

## **5 Appendix**

### **5.1 Imputation rules**

#### **5.1.1 Study drug**

Missing/partial start date or end date of double-blind treatment will not be imputed.

#### **5.1.2 AE date imputation**

Partial AE start and end dates will be imputed. If there is uncertainty whether an AE occurred treatment-emergent or not, imputation will be performed, such that AE will be considered as treatment-emergent. Rules for imputing AE end date or start date will be provided in Programming Dataset Specification (PDS) document in details.

#### **5.1.3 Concomitant medication date imputation**

Rules for imputing the CM end date or start date will be provided in PDS document in details.

### **5.2 AEs coding/grading**

The MedDRA version which will be available at the time of database lock, will be used for the coding purpose of the adverse events.

### **5.3 Laboratory parameters derivations**

Grade categorization of lab values will be assigned programmatically as per Common Terminology Criteria for Adverse Events (CTCAE) version 5.0.

A severity grade of 0 will be assigned for all non-missing lab values not graded as 1 or higher. CTCAE Grade 5 is not defined for laboratory values.

### **5.4 Statistical models**

#### **5.4.1 Primary analysis**

The null hypothesis for the primary analysis is that there is no difference in the proportion of patients meeting the primary composite endpoint between ruxolitinib + SoC and placebo + SoC treatment groups. The alternative hypothesis is that there is a difference between the two treatment groups.

The null hypothesis will be tested using a logistic regression model with treatment, age, gender, region, and baseline clinical status based on the 9-point ordinal scale ( $\leq 3$ ,  $\geq 4$ ) as covariates.

The SAS procedure LOGISTIC will be used to conduct the analysis.

The estimated odds ratio, associated two-sided 95% confidence interval, and two-sided p-value will be presented for treatment contrasts between ruxolitinib + SoC and placebo + SoC.

In case of separability, Firth's penalized maximum likelihood estimation will be performed. The SAS macro %fl ([Heinze and Ploner 2004](#)) will be used for performing the estimation.

- **Sensitivity analysis of the primary endpoint**

Non-parametric analysis

In order to determine the robustness of the logistic regression model used for the primary analysis, nonparametric randomization-based analysis of covariance model (Koch et al 1998) will be evaluated using the same covariates as in the primary analysis model.

A SAS macro (%NParCov4) has been developed to facilitate the implementation of this analysis (Dmitrienko and Koch 2017).

To test the treatment effect, the most appropriate variance matrix is the one that applies to the randomization distribution under the null hypothesis of no treatment differences: a first model will be obtained using this assumption (i.e. parameter HYPOTH = NULL).

It is also of interest to obtain CI for the odds ratio. The most appropriate variance matrix in this case is the one that applies under the alternative: a second model will be obtained using this assumption (i.e. parameter HYPOTH = ALT).

Risk difference based on the marginal standardization method

The sensitivity analysis will assess the between group comparison based on the risk difference using the marginal standardization method. The estimated risk difference can be derived from a logistic regression model fit to the binary outcome variable with the same covariates as in the primary analysis model. The fitted logistic regression model is used to predict the response risk for every subject in the study as if they had received ruxolitinib + SoC or placebo + SoC, and the difference in risks between treatment groups is computed. The delta method is used to calculate a standard error for the difference.

The method will be implemented using SAS macro (%margins) or the SAS macro provided in the paper by Ge et al 2011.

- **Multiple imputation for supplementary analysis**

For supplemental analysis the following imputation steps need to be performed for missing data. Missing data of the composite endpoint will be imputed using J2R assumption for the ruxolitinib + SoC arm and MAR assumption for placebo arm.

1. Impute missing data:

Select all patients, impute missing values using the MI approach based on the logistic regression method for 100 times and obtain 100 imputed datasets. A pattern-mixture model approach (Ratitch and O’Kelly 2011) that uses a control-based pattern imputation will be implemented. That is, an imputation model for the missing observations in the ruxolitinib + SoC group is constructed not from the observed data in the ruxolitinib + SoC group but rather from the observed data in the placebo + SoC group. This model is also the imputation model that is used to impute missing observations in the placebo + SoC group. The imputation model will include age, gender, region, BMI ( $\leq 30.0 \text{ kg/m}^2$ ,  $> 30.0 \text{ kg/m}^2$ ), and baseline clinical status (assessed by the 9-point ordinal scale) as predictors. If any of these predictors cause separability issues for the logistic regression, the levels of the predictors will be combined accordingly.

This results in 100 imputed datasets.

2. The primary composite endpoint will be analyzed (by imputed dataset) using the final multiply-imputed dataset where all missing values are filled, using a logistic regression model with treatment, age, gender, region, and baseline clinical status (assessed by the 9-point ordinal scale) as predictors.
3. The results for the treatment effect from the 100 datasets will then be combined using Rubin's rule.

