12.4.7 Supportive analyses

The primary analysis of the clinical failure will be repeated for each of the events in the composite endpoint: occurrence of death, mechanical ventilation, and ICU care. Separate logistic regression models will be fitted to compare the odds between treatment groups for each of the endpoints. The analysis will be performed for both Days 15 and 29.

As there is uncertainty around the covariates to be included in the primary analysis model for the clinical failure by Day 29, analyses will be performed considering additional covariates, for example, co-morbidities. These analyses will be defined further in the study analysis plan.

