**Figure 1-1 Study design**

Eligible patients will be randomized on the same day as screening or up to two days after completing the screening procedures. At Day 1 (randomization visit), patients will be assigned in a 2:1 ratio to receive oral ruxolitinib 5 mg twice daily or oral matching-image placebo for a total of 14 days. An additional 14 days of study drug may be given, if in the opinion of the

investigator, the patient's clinical signs and symptoms are neither improved nor worsened and the potential benefit outweighs the potential risk.

Approximately 402 patients in total are needed (268 randomized to ruxolitinib and 134 to placebo). Detailed information regarding sample size calculation is provided in [Section 3](#).

Randomization will be stratified by geographic region (North America, West Europe, East Europe, Latin America, and Other).

The primary endpoint will be assessed over 29 days.

No interim analysis is planned. A Data Monitoring Committee (DMC) at Novartis will be established to conduct periodical unblinded safety reviews. The analysis plan for the DMC will be created separately.

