#### **2.7.1.2 Oxygen saturation**

The proportion of patients with no oxygen therapy (defined as having a clinical status score of 0, 1, 2, or 3, or oxygen saturation  $\geq 94\%$  when measured on room air) at Days 15 and 29 will be analyzed using logistic regression models with the same covariates as for the primary analyses, with baseline SpO2/FiO2 added. The estimated odds ratios, p-values, and 95% CIs will be presented.

Missing data at Day 15/29 will not be imputed and thus will be excluded from the analysis.

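### The primary model's only severity term is clinical status cut at ≤3 / ≥4; adding baseline SpO2/FiO2, already collected, would be a modest and cheap efficiency gain

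*SAP*

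**What the plan says.** SAP 2.5.2 and 5.4.1 specify "a logistic regression model with treatment, age, gender, region, and baseline clinical status based on the 9-point ordinal scale", with status split at ≤3 and ≥4. SAP Section 4 explains that the protocol's split (≤4, ≥5) was moved because few patients entered at score 5. On the scale in SAP 2.7.1.1, score 3 is hospitalised without oxygen, 4 is oxygen by mask or prongs, and 5 is non-invasive ventilation or high-flow oxygen. The new split therefore pools 4 and 5.

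Protocol Table 8-1 schedules SpO2 and FiO2 at screening and Day 1, with eCRF entry. Protocol Section 8 requires oxygen saturation and ventilatory status to be assessed before the first dose on the day of randomization. SAP 2.3.2 summarises SpO2/FiO2 as a baseline characteristic. SAP 2.7.1.2 models the no-oxygen-therapy endpoint with "logistic regression models with the same covariates as for the primary analyses, with baseline" SpO2/FiO2 added.

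Protocol 12.4.7 begins "As there is uncertainty around the covariates to be included in the primary analysis model" and promises supportive analyses with additional covariates, naming co-morbidities as an example and leaving the detail to the SAP. SAP 2.5.4 defines no such analysis apart from subgroup models with interactions, and SAP Section 4 does not list it as dropped.

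**The concern.** The composite measures respiratory deterioration. Among patients on oxygen at entry, need can run from a low-flow cannula to non-invasive ventilation, and the planned model treats them as equally severe. If baseline oxygenation predicts the outcome within that group, leaving it out gives up some power, and a chance imbalance in oxygenation between 268 and 134 patients goes uncorrected in the estimate. The thin numbers at score 5 that led to the new cut are a reason to prefer a continuous measure over a category.

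**Working it through.** **1. The plan's own power.** SAP Section 3 states that "a sample size of approximately 402 participants provides at least 80% power", for a result "statistically significant at the two-sided 5% significance level", with a 15-point difference; SAP 1.1 gives "268 randomized to ruxolitinib and 134 to placebo". With unpooled variance:

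SE = √[p0(1−p0)/134 + p1(1−p1)/268]; power = Φ(|p0−p1|/SE − 1.96).

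At 50/35: SE = √(0.25/134 + 0.2275/268) = 0.0521; 0.15/0.0521 = 2.879; power = Φ(0.919) = 82.1%.

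| Placebo / ruxolitinib (%) | Stated (%) | Recomputed (%) |
|---|---|---|
| 80/65 | 91 | 91.3 |
| 70/55 | 85 | 85.2 |
| 60/45 | 82 | 82.1 |
| 50/35 | 82 | 82.1 |
| 40/25 | 85 | 85.2 |
| 30/15 | 91 | 91.3 |

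All six rows reproduce. The formula has no covariate in it.

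**2. Gain from adding the ratio, complete data.** Simulation of 402 patients, 2:1, two-sided Wald test at 5%, 4,000 trials per scenario, marginal rates held at the SAP Table 3-1 values. The planned model was represented by treatment, two-level status and age; region and gender were left out. Assumptions not in the documents: log odds 0.7 for status and 0.4 per SD of age; about 69% of patients at status ≥4; correlation 0.7 between the ratio and the scale underlying status; odds ratio (OR) per SD of the ratio, given the other terms, of 1.0 to 3.0.

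| OR per SD | 50/35: planned → with ratio (%) | 30/15: planned → with ratio (%) |
|---|---|---|
| 1.0 | 84.7 → 84.7 | 93.5 → 93.5 |
| 1.5 | 85.7 → 86.4 | 94.4 → 95.1 |
| 2.0 | 86.2 → 88.4 | 94.4 → 95.7 |
| 3.0 | 87.6 → 92.1 | 94.7 → 96.9 |

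At 50/35 and OR 3.0, the gain is 5.9 points if the correlation is 0.4 and 3.0 points if it is 0.9. With no treatment effect (30/30, OR 2.0), rejection was 5.2% for the planned model and 5.0% with the ratio. The Monte Carlo standard error of a single power near 85% is √(0.85 × 0.15/4000) = 0.6 points; both models were fitted to the same simulated data, so the differences are steadier than that.

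**3. Missing ratios.** Same set-up at 50/35, 3,000 trials per scenario, ratios missing at random:

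| Log OR per SD | Missing | Planned (%) | With ratio, median rule (%) | With ratio, complete cases (%) |
|---|---|---|---|---|
| 0.5 | 10% | 85.3 | 86.4 | 83.2 |
| 0.8 | 10% | 86.3 | 89.4 | 86.9 |
| 0.8 | 20% | 85.5 | 88.1 | 80.4 |

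The gains under the median rule are 1.1, 3.1 and 2.6 points. If the ratio has no prognostic value, power changes by no more than 0.1 point under the median rule. At 30/15 the largest gain found was about 1.6 points. With no treatment effect, rejection was 5.4% planned and 5.5% with the median rule.

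The cost of dropping patients also shows in the formula of step 1. At 50/35, reducing both arms by 5% gives 80.1% and by 10% gives 78.0%, losses of 2.0 and 4.1 points from 82.1%.

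**The case against.** The strongest reply is that this is a choice of efficiency. The planned power needs no covariate, the planned adjusted model already reaches about 85 to 88% at 50/35 in simulation, and type I error is sound either way. All of that stands. The sampling variation behind a chance imbalance is also already reflected in the confidence interval.

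Second, the size of the gain is assumed. It is under 1 point unless the OR per SD, beyond status and age, exceeds about 1.5. Score 3 means SpO2 of at least 94% on room air, so taking FiO2 as 0.21 the ratio there lies only between 94/0.21 = 448 and 100/0.21 = 476. New information comes almost wholly from patients at scores 4 and 5, whereas the simulation let the covariate vary in both status levels. The simulated gains may therefore be somewhat generous.

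Third, the change is not free. For patients on oxygen, Protocol 8.3.2 accepts flow rate, FiO2 or both, and the SAP gives neither a conversion nor a missing-baseline rule for the ratio. This stands and shapes the fix. FiO2 will be missing mainly in patients on oxygen, so a whole-sample median would blur the contrast being sought; a median within status level is better. The SAP needs a derivation anyway, because SAP 2.3.2, 2.7.1.2 and 2.7.1.5 all use the ratio.

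Fourth, a reader might infer that the SAP contradicts itself by using the ratio for one endpoint and not the other. It does not: the oxygen and NEWS2 models each add a baseline close to their own outcome, and the composite has no such baseline. Likewise, Protocol 12.4.7 commits the sponsor to additional-covariate supportive analyses. It does not name SpO2/FiO2 or promise to change the primary model.

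**Conclusion.** The point holds as a cheap improvement. The primary model has no severity contrast among patients on oxygen, and the trial already collects and derives a continuous baseline measure that could supply one. The gain is 0 to about 6 power points over the assumed range. It is about 1 to 3 points at 50/35 for log odds ratios per SD of 0.5 to 0.8 with 10% missing and a median rule, and less at 30/15. There is no material loss if the ratio is uninformative.

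Two stronger readings are tempting. One is that the primary test is invalid or the trial underpowered. SAP Table 3-1 reproduces in full without any covariate, and simulated type I error stays near 5%. The other is that power is certainly being lost and could be recovered at no cost. The documents give no prognostic strength for the ratio beyond the planned covariates, and the incomplete recording of FiO2 has to be dealt with first.

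**What to change.** Before unblinding, and listed in SAP Section 4:

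- Add baseline SpO2/FiO2 (last value before first dose, linear term) to the primary logistic model, and to the non-parametric sensitivity, marginal-standardisation and multiple-imputation models that share its covariates.
- State how FiO2 is derived when only flow rate is recorded.
- Impute a missing baseline ratio by a rule blind to treatment, for example the median within baseline clinical-status level. SAP 2.7.1.1 already uses a median rule for missing clinical status. Do not fit complete cases only.
- Say whether the secondary models defined by reference to the primary covariates (SAP 2.7.1.1, 2.7.1.3 and 2.7.1.4) take on the new term as well.

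The cost is one degree of freedom and two rules to write; no new data are needed. If the sponsor prefers to leave the primary model alone, the least change is to specify this model as the additional-covariate supportive analysis promised in Protocol 12.4.7.

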#### **5.4.2 Key secondary analysis**

There is no key secondary analysis defined in the protocol.

## 5.5 Rule of exclusion criteria of analysis sets

The following table provides the protocol deviations (PD) and other criteria leading to partial or complete exclusion from the analyses sets.

Deviation ID	Description of Deviation
Deviations leading to exclusion from RAS and Safety set	
INCL01B	Patient or guardian / health proxy did not sign informed consent

## 5.6 Type of pulmonary/ventilatory support

**Table 5-1 Type of pulmonary/Ventilatory support based on the level of oxygen requirement from low to high**

Type of support	Require supplemental oxygen	Require (invasive) mechanical ventilation
Low flow nasal oxygen	Yes	No
High flow nasal oxygen	Yes	No
Oxygen via face mask	Yes	No
Non-invasive ventilation	Yes	No
Mechanical ventilation	Yes	Yes
Intubation	Yes	Yes
Tracheostomy	Yes	Yes
ECMO	Yes	Yes

